1.35 Inclusion of Women and Minorities

The study site should aim and take steps to enroll a diverse study population. If difficulty is encountered in recruiting an adequate number of women and/or minorities, the difficulties involved in recruitment will be discussed with study staff.

1.36 Regulatory Files

The regulatory files should contain all required regulatory documents, study-specific documents, and all-important communications. Regulatory files will be checked by the LI for regulatory document compliance prior to study initiation, throughout the study, as well as at study closure. Upon study end, the LI will ensure that all documentation complies with regulatory requirements and that analysis of identifiable information has been completed prior to submitting to the Yale IRB for study closure.

1.37 Records Retention and Requirements

Research records for all study participants (e.g., case report forms, source documents, signed consent form, and regulatory files) are to be maintained by the investigator in a secure location for a minimum of 3 years after the study is completed and closed. While the Hugo platform will have real-time access to participant-shared data for up to one-year from enrollment, the data downloaded for the purposes of this study is considered a research record and will be maintained for the same duration as other study materials. These records are also to be maintained in compliance with IRB, state and federal requirements, whichever is longest. The funder must be notified in writing and acknowledgment must be received by the site prior to the destruction or relocation of research records.

1.38 Reporting to Funder

The Lead investigator agrees to submit accurate, complete, legible and timely reports to the funder, as required. These include, but are not limited to, reports of any changes that significantly affect the conduct or outcome of the study or increase risk to study participants. Given the short duration of the study, safety reporting will occur as needed (if applicable, as described elsewhere in this protocol) and at the end of the study. At the completion of the trial, the Lead Investigator will provide a final report to the funder.

1.39 Audits

The Funder has an obligation to ensure that this trial is conducted according to good research practice guidelines and may perform quality assurance audits for protocol compliance. The Lead Investigator and authorized staff from the New England Consortium Node; the National Institute on Drug Abuse Clinical Trials Network (NIDA CTN, the study funder); NIDA's contracted agents, monitors or auditors; and other agencies such as the Department of Health and Human Services (HHS), the Office for Human Research Protection (OHRP) and the Institutional Review Board of record may inspect research records for verification of data, compliance with federal guidelines on human participant research, and to assess participant safety.

1.40 Study Documentation

The site will maintain appropriate study documentation (including medical and research records) for this trial, in compliance with ICH E6 and regulatory and institutional requirements for the protection of confidentiality of participants. Study documentation includes all completed assessments, surveys, approved protocol and amendments, Ethics Review Committee or Institutional Review Board correspondence and approved consent form and signed participant consent forms. As part of participating in a NIDA-funded study, each site will permit authorized representatives from NIDA and regulatory agencies to examine (and when permitted by law, to copy) clinical records for the purposes of quality assurance reviews, audits, and evaluation of the

study safety, progress, and data validity.

Source documents include all recordings of observations or notations of clinical activities and all reports and records necessary for the evaluation and reconstruction of the clinical research study. Whenever possible, the original recording of an observation should be retained as the source document; however, a photocopy is acceptable provided that it is a clear, legible, and exact duplication of the original document.

1.41 Protocol Deviations

Any departure from procedures and requirements outlined in the protocol will be classified as either a major or minor protocol deviation. The difference between a major and minor protocol deviation has to do with the seriousness of the event and the corrective action required. A minor protocol deviation is considered an action (or inaction) that by itself is not likely to affect the scientific soundness of the investigation or seriously affect the safety, rights, or welfare of a study participant. Major protocol deviations are departures that may compromise the participant safety, participant rights, inclusion/exclusion criteria or the integrity of study data and could be cause for corrective actions if not rectified or prevented from re-occurrence. The site will be responsible for developing corrective action plans for both major and minor deviations as appropriate. Those corrective action plans may be reviewed/approved by the Lead Node and NIDA or NIDA designee, with overall approval by the IRB of record. All protocol deviations will be monitored at the site for (1) significance, (2) frequency, and (3) impact on the study objectives, to ensure that site performance does not compromise the integrity of the trial.

1.42 Safety Monitoring

1.42.1 Data and Safety Monitoring Board (DSMB)

As a minimal-risk study, the study does not require an independent NIDA CTN DSMB. However, a detailed Data and Safety Monitoring Plan (DSMP) is included as an appendix, which incorporates requirements of both the Yale IRB and NIDA CTN.

1.42.2 Adverse Events (AEs)

As a minimal risk observational, non-medication intervention study, we will only collect information as reported through the EHR and the PRO and not specifically collect adverse event or serious adverse event information. The Lead Investigator will be responsible for the management of information gathered by the RAs and develop processes and procedures at the site for that management. The LI will designate a backup in the event she will not be available. The appropriate response and action will be determined in collaboration with the LI, Yale IRB and funder and carried out by the appropriate party.

DATA MANAGEMENT

1.43 Site Responsibilities

Data oversight will be conducted by study team members at Yale School of Medicine in collaboration with Hugo. Hugo is responsible for maintaining and securely transferring all electronic data captured through their tool, which includes survey responses, EHR data and pharmacy data, outlined in this protocol. Yale is responsible for conducting ongoing data monitoring activities and performing data cleaning and all data analysis.

1.44 Data Collection and Security

Hugo:

Participants will be requested to submit data from their personal health records to the study over SSL with a minimum of 128-bit encryption. This data will be downloaded to a secure server with Yale with access available only to study personnel for one year following enrollment. Data will be received from the Hugo platform at scheduled intervals via secure webservice endpoint and stored on a password-protected encrypted university computer or secure university server and stored for the duration of the study. The Hugo platform has undergone a thorough security analysis by Yale University to ensure its safety and confidentiality and details regarding their data management are included in the attached Hugo Security Statement and Privacy Notice.

Yale:

Paper files, such as signed consent forms, will be in locked files in the Emergency Department's research room. All study data will be stored on secure university-maintained computers and servers, with restricted access to investigators and staff listed on this protocol. All data will be transferred over encrypted connections and stored on Yale or YNHHS-managed hardware that is suitable for PHI. Data will also be transferred with Yale-managed IronKey encrypted portable devices. Only study personnel directly involved in data analysis with a need to access PHI will have access to these data. After the completion of study enrollment, all data will be de-identified for ongoing analysis and patients will only be identified by study ID. However, study records will be maintained for three years per IRB guidelines, after which paper documents will be destroyed. Following the data lock, electronic data will be de-identified and shared the NIDA Data Share website, as outlined in this protocol.

When research assistants travel between YSC and SRC, they will utilize the YNHHS interfacility shuttle and will keep all study devices (i.e., laptop and tablet), signed consent forms, and any other documentation with PHI on their person, or locked in the YSC or SRC research rooms at all times.

PUBLICATIONS AND OTHER RIGHTS

Per NIH policy, the results of the proposed trial are to be made available to the research community and to the public at large. The planning, preparation, and submission of publications will follow the policies of the Publications Committee of the CTN.

PROTOCOL SIGNATURE PAGE

FUNDER'S REPRESENTATIVE (CCTN SCIENTIFIC OFFICER OR DESIGNEE)

Printed Name	Signature	Date

APPENDIX B: DATA AND SAFETY MONITORING PLAN

1.0 BRIEF STUDY OVERVIEW

The goal of this project is to enhance capacity to use EHR data and PROs to conduct opioid-related research in EDs. For this project, Hugo will be used to explore the feasibility and usability of electronic PRO measurement through patient portals.

2.0 OVERSIGHT OF CLINICAL RESPONSIBILITIES

A. Lead Investigator

The Lead Investigator is responsible for monitoring the data, assuring protocol compliance, and conducting the safety reviews. During the review process the Lead Investigator will evaluate whether the study should continue unchanged, require modification/amendment, or close to enrollment. The LI will monitor the protocol for integrity and operations through several means. First, the LI will directly observe initial patient enrollments by trained research assistants. In addition, case-by-case feedback regarding enrollment and participation will be conducted for the first 10 enrollments to ensure no protocol violations or unexpected issues. Given the short-period of this study, the LI will also be available by phone during all enrollment times to provide additional support and resources for any challenges encountered during the study period.

The LI, the Institutional Review Board (IRB) and funder (National Institutes of Health) have the authority to stop or suspend the study or require modifications.

This protocol presents minimal risks to the subjects and Unanticipated Problems Involving Risks to Subjects or Others (UPIRSOs), including adverse events, are not anticipated. In the unlikely event that such events occur, Reportable Events (which are events that are serious or life-threatening and unanticipated (or anticipated but occurring with a greater frequency than expected) and possibly, probably, or definitely related) or Unanticipated Problems Involving Risks to Subjects or Others that may require a temporary or permanent interruption of study activities will be reported immediately (if possible), followed by a written report within 5 calendar days of the Lead Investigator becoming aware of the event to the IRB (using the appropriate forms from the website) and any appropriate funding and regulatory agencies. The investigator will apprise fellow investigators, study personnel and funders of all UPIRSOs and adverse events that occur during the conduct of this research project via regular study meetings or email, as appropriate, within 5 days becoming known to the Lead Investigator.

B. Management of Risks to Participants

Confidentiality

Confidentiality of participant records will be secured using study codes for identifying participants, and secure storage of any documents that have participant identifiers on site, as well as secure computing procedures for entering and transferring electronic data. The documents or logs linking the study codes with the study participant on site will be kept locked separately from the study files and the medical records. No identifying information will be disclosed in reports, publications or presentations.

Information That Meets Reporting Requirements

The consent form will specifically state the types of information that are required for reporting and that the information will be reported as required. These include suspected or known sexual or physical abuse of a child or elders, or threatened violence to self and/or others.

Participant Protection

The RA will be adequately trained by the LI to ensure that all participants are eligible and safe to enter the study. When necessary, the RA will obtain guidance from ED providers and/or LI when in need of any guidance on inclusion/exclusion criteria and/or safety concerns.

Pregnancy

As there is no medication intervention, pregnancy will not be followed within the context of this study.

Study Specific Risks

The risks associated with this study are minimal and include loss of privacy or confidentiality, potential increased length of stay in the Emergency Department, and potential inconvenience and discomfort answering surveys, which include questions about drug use. The risk to patient privacy is no different with this study than it is with any other study that securely collects and appropriately stores personally identifiable information or protected health information. Indeed, the risk may be less since researchers are only getting access to patient data from the time of enrollment forward for 1 year; there is no open access to the patient's entire medical record. The Hugo S4S platform, like many other personal health records, is not a covered entity; therefore, the HIPAA privacy rule does not apply to this platform. The Hugo platform does take all necessary precautions, including industry-standard encryption of data in transit and at rest, to minimize privacy and security risks to personally identifiable information and PHI stored on behalf of study participants.

To address the risks above, patient privacy and confidentiality will be respected at all times and a private area will be arranged for patient screening, enrollment and interviews when feasible. Study enrollment should not delay discharge from the Emergency Department, and if the patient is otherwise ready for discharge upon study enrollment, they will be given the option to not participate. In respect to minimizing risks for data exposure, all patient data will be collected, handled, and stored according to the most rigorous accepted standards. Staff involved in the study will be appropriately trained to maximize data security and technical systems will meet or exceed requirements imposed by HIPAA. Sensitive information will always be encrypted in transit and at rest. Paper files will be in locked files in the Emergency Department's research room.

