1.4 Assessment and Duration

The duration of active participation in this study is one month and includes a baseline, one week and 30-day electronic survey. However, researchers will have access to participants’ EHR and pharmacy data through Hugo for up to one year after enrollment. The study is estimated to last one year, which includes enrollment and follow-up, data analysis, and manuscript development as outlined below.

3/1/2019 - 4/1/19	Yale IRB Submission/Approval
4/2/19 - 4/12/2019	OHRP Approval
4/15/2019 - 4/30/19	Pilot Enrollment (10 subjects)
5/1/2019 - 10/31/19	Full-time Enrollment (190 subjects)
10/31/19 - 12/31/19	Follow-up Completion (Surveys and EHR extraction)
1/1/20 - 2/28/20	Data Cleaning, Lock, Analysis
3/1/19 - 5/29/20	Manuscript Development

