In addition, Hugo will automatically pull select data fields from each participant's shared records (EHR and pharmacy data) on a weekly basis. The infrastructure and agreements for secure data sharing between EHRs and pharmacies with Hugo are already established and occur automatically once patients link their accounts. Researchers will have access to data fields via Hugo for one year after enrollment for each participant and Hugo will send data fields to Yale via secure file transfer every two weeks or as needed. Access to data fields is permitted for one year to ensure that researchers have access to all participants data from the start of enrollment through analysis completion, should it be needed. Therefore, patients consent to sharing data for one year, although those enrolled later in the study will not be sharing data for the entire year. Survey, EHR and pharmacy data will be used to assess the study outcomes outlined above.

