1.12 Duration of Study Schedule

Each subject will be actively on study until surveys are completed or until end of study eligibility period. Their passive participation in data sharing will last one year following enrollment.

OUTCOME MEASURES

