1.16 Study Timeline

After receiving funder approval of the final protocol, Institutional Review Board (IRB) approval will then be obtained from the Yale University IRB. Once approved, enrollment will take place in the following year until up to 200 patients are enrolled or if the study enrollment time period ends per funding and program duration. Enrollment will be rolled out slowly, with an initial pilot period of up to one month. During this time, up to ten patients will be enrolled to ensure proper functionality of the Hugo tool, PRO delivery, EHR integration and data transfer. Their data will be included in the final data analysis.

Once all surveys and follow-up are complete for the study, EHR data collection will be finalized within two months of the final participant enrollment. Therefore, data lock is projected to occur approximately 12 months after IRB approval.

STUDY POPULATION

The study population consists of adult ED patients with OUD or non-medical opioid use, or those who are being treated for opioid overdose.

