5. EHR Data Extraction: In addition to survey data, the following fields will be automatically extracted from participants EHRs: Name, Age, Gender, Date of birth, Medical record number, Vital signs, Provider encounters, Family history, Laboratory findings, Procedures, Problem list, ICD diagnoses, Medicines administered and prescribed. These fields will be used for secondary and/or future exploratory analyses as they relate to PROs and can be extracted as far back as each participant's available EHR.
6. Pharmacy Data Extraction: Prescription refill data will be automatically extracted from participating pharmacies that currently share data with Hugo, such as CVS and Walgreens, and are linked to each participant's Hugo account. Available prescription data will be used for secondary and/or future exploratory analyses as it relates to PROs.
7. Case Report Form – Enrollment: Used to document whether participants required assistance setting up a MyChart or pharmacy account to be linked with Hugo.

8. Case Report Form – Follow-up Call: Used to document information collected during follow-up calls, when applicable.

TRAINING REQUIREMENTS

All study personnel such as LI, co-lead investigators, study RA, project managers and data analysts will be listed on the Yale IRB submission. Per Yale IRB policies, all staff must have completed HIPAA training, Human Subjects Protection Training, Good Clinical Practice Training and a conflict of interest form (investigators only) for the submission to be approved. In addition to these trainings, the LI will provide protocol specific training and ensure that all staff understand the study protocol and follow all guidelines outlined in this document.

STATISTICAL DESIGN AND ANALYSES

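### The protocol allows EHR fields to be extracted from a participant's whole available history, but its risk statement says researchers see data only from enrollment forward

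*Protocol*

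**What the plan says.** **Start of the EHR window.** Two places in the Protocol address it.

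- Study Assessments, item 5 (EHR Data Extraction), lists the fields pulled automatically. They include name, date of birth, medical record number, problem list, diagnoses, laboratory findings and medicines. The fields are meant for secondary or future exploratory analyses and "can be extracted as far back as each participant's available EHR".
- Appendix B, 2.0 B, Study Specific Risks, says that "researchers are only getting access to patient data from the time of enrollment forward for 1 year", and continues that "there is no open access to the patient's entire medical record". The sentence is given in support of the statement that the risk to privacy may be less than in other studies that hold such data.

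Section 1.11 (Data Management) adds that the platform pulls selected fields automatically every week once accounts are linked.

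**End of the window.**

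- Section 1.4: "researchers will have access to participants’ EHR and pharmacy data through Hugo for up to one year after enrollment".
- Section 1.11: "Researchers will have access to data fields via Hugo for one year after enrollment for each participant". The same paragraph calls this permitted access, meant to last through completion of the analysis, and says that later enrollees will share for less than the full year.
- Section 1.12: "Their passive participation in data sharing will last one year following enrollment", without qualification.
- Section 1.16: "EHR data collection will be finalized within two months of the final participant enrollment".
- Section 1.37 again treats one year as a maximum.

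**The concern.** The two statements on the start of the window give opposite answers to a simple question: may a record dated before enrollment reach the research team? Item 5 says it may, with no limit. The risk statement says it may not.

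Two things depend on the answer.

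1. **The accuracy of the risk statement.** The participants have opioid use disorder, non-medical opioid use or an overdose, and the protocol says that the platform is not subject to HIPAA. If identified historical fields are extracted, the oversight plan describes a restriction that does not exist and draws reassurance from it.
2. **Which data may be analysed.** If the risk statement is the rule, prior diagnoses, medicines and encounters are not available for the analyses that item 5 has in mind.

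Because the pull is automatic and weekly, the question is settled in practice as soon as a participant links an account, whichever text was intended.

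**Working it through.** **Start of window.** No arithmetic applies, so the texts are compared directly.

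| | Study Assessments, item 5 | Appendix B, 2.0 B |
|---|---|---|
| Earliest record | Oldest in the available EHR | Date of enrollment |
| Look-back | Unlimited | None |
| Use made of the statement | Source for secondary or exploratory analyses | Reason for a lower privacy risk |

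1. Suppose item 5 governs. Records from before enrollment are extracted in the listed fields. The restriction to enrollment forward in Appendix B is then untrue, and so is the reason it gives for lower risk.
2. Suppose Appendix B governs. No record from before enrollment may be extracted, and the permission in item 5 is void.
3. Sections 1.4, 1.11, 1.12 and 1.37 all deal with how long access runs after enrollment. None says how far back the records may go, so none resolves the conflict.

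**End of window.** Inputs from the section 1.4 timeline: first pilot enrollment 4/15/2019, last enrollment 10/31/2019, EHR extraction complete 12/31/2019.

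1. Reproducing the cut-off of two months in section 1.16: 10/31/2019 to 12/31/2019 = 30 + 31 = 61 days. The section agrees with the timeline.
2. Longest forward window: 4/15/2019 to 12/31/2019 = 15 + 31 + 30 + 31 + 31 + 30 + 31 + 30 + 31 = 260 days.
3. Shortest forward window: 61 days (last enrollee).
4. Carried to 2/28/2020, the end of cleaning, lock and analysis (31 + 28 = 59 more days): 260 + 59 = 319 and 61 + 59 = 120 days.
5. Carried to 12 months after IRB approval, which section 1.16 projects for data lock (assuming approval on 4/1/2019, so 4/1/2020): 352 and 153 days.

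Nobody reaches 365 days by any of these dates. Section 1.11 ascribes the shortfall to later enrollees only, whereas on these dates it applies to everyone. That is loose wording. A ceiling of one year is still compatible with a collection period that ends sooner.

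**The case against.** **On the look-back.** The best defence has four parts.

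- *Item 5 is permissive.* It says what can be extracted, and no named analysis uses history. It is true that no planned analysis is shown to fail. But permission to extract history is access to history, which the risk statement rules out.
- *The risk statement describes the period of access, as section 1.37 does, and not the dates of the records.* This does not work in context. The sentence offers the limit as a restriction on the data obtained; otherwise it would be no reason for lower risk.
- *A closed list of fields is not open access to a whole chart.* This stands. The clause "there is no open access to the patient's entire medical record" can be squared with item 5, so the contradiction rests on the clause before it.
- *The minimal-risk classification does not rest on this sentence.* This also stands. Appendix B first says that the risk is the same as in any study holding such data securely. Only the further argument that it may be lower falls.

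**On stronger readings.** A reader might infer that the end of the window is contradictory too, with one year promised to everyone against a cut-off two months after the last enrollment. The protocol does not support this. Sections 1.4 and 1.37 make one year a maximum, section 1.11 calls it a permission and says that some will share for less, and the cut-off fits the timeline.

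A reader might also infer that forward windows of 61 to 260 days bias prescription or treatment outcomes by enrollment date. Sections 1.6, 1.9 and 1.14 list those outcomes as survey measures, timed within one week and at 30 days. Section 1.11 does say in general terms that EHR and pharmacy data will be used to assess outcomes, but it specifies no EHR endpoint. A window for such variables can properly be left to the SAP, so there is no ground for requiring a common 30-day EHR window.

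**Conclusion.** The protocol contradicts itself on whether EHR records from before enrollment are obtained, and the risk statement in Appendix B cannot stand alongside Study Assessments, item 5. The difference is between no look-back and the full available record in the listed fields, for each of about 200 participants.

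This is an inconsistency of moderate weight. It affects what is extracted, or what the oversight plan says about risk. The primary outcomes (enrollment, survey response and loss to follow-up) are counted the same way under either text.

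Two limits apply. The consent form is not among the documents, so it cannot be concluded that participants were misinformed. Nor do the documents show which window was intended or how the feed was configured.

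At the end of the window only a wording point remains: section 1.12 states a full year without the qualification given in sections 1.4, 1.11 and 1.37.

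**What to change.** 1. Choose one look-back and state it in the same terms in Study Assessments, item 5, and Appendix B, 2.0 B. Either
   - limit the extraction to records from enrollment forward and remove the unlimited look-back from item 5; or
   - keep the look-back, correct Appendix B to say that selected historical fields are extracted, and delete the argument that the risk may be lower.
2. Check that the consent form describes the same window.
3. Until this is settled, keep the automatic feed to the narrower window (enrollment forward).
4. As a minor wording change, have section 1.12 give one year as the maximum period of sharing, in line with sections 1.4, 1.11 and 1.37.

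The cost is a short amendment and a consent check. The first option gives up historical fields for exploratory use. The second gives up one sentence of reassurance. Neither changes the sample size, the surveys or the primary outcomes.
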